## 1 GLOSSARY OF TERMS

Names of Test Product(s)	Throughout this document, test product TOTAL30 Multifocal for Astigmatism will be referred to as T30 MFfA.
Name of Comparator Product(s)	Throughout this document, comparator product ULTRA® Multifocal for Astigmatism will be referred to as ULTRA MFfA.
Adverse Device Effect (ADE)	
Adverse event related to the use of an investigational medical device or comparator.
 
Note: This definition includes adverse events resulting from insufficient or inadequate instructions for use, deployment, implantation, installation, or operation; any malfunction; and use error or intentional misuse.

Adverse Event (AE)	
Untoward medical occurrence, unintended disease or injury, or untoward clinical signs (including abnormal laboratory findings) in subjects, users, or other persons, whether or not related to the investigational medical device or comparator and whether anticipated or unanticipated.
 
Note: For subjects, this definition includes events related to the investigational medical device, comparator, or the procedures involved. For users or other persons, this definition is restricted to the use of the investigational medical device or comparator.
 
Requirements for reporting adverse events in the study can be found in Section 11.

Anticipated Serious Adverse Device Effect (ASADE)	An effect which by its nature, incidence, severity, or outcome has been identified in the risk assessment.

Clinical Investigation Plan (CIP)	
The document(s) stating the rationale, objectives, design, and prespecified analysis, methodology, organization, monitoring, conduct, and record-keeping of the clinical investigation.
 
Note: The protocol and other documents referenced in the protocol (for example, the SAP, the MOP, the DEP, and the Protocol Monitoring Plan) comprise the CIP.

Clinical Investigation Report (CIR) / Clinical Study Report	
The document describing the design, execution, statistical analysis, and results of a clinical investigation. The clinical investigation report is synonymous with the clinical study report.

Device Deficiency	
Inadequacy of a medical device with respect to its identity, quality, durability, reliability, usability, safety, or performance.
 
Note: This definition includes malfunctions, use errors, and inadequacy in the information supplied by the manufacturer including labelling related to the investigational medical device or the comparator.
 
Requirements for reporting device deficiencies in the study can be found in Section 11.

Enrolled Subject	
Any subject who signs an informed consent form for participation in the study.

Point of Enrollment	
The time at which, following recruitment and before any clinical investigation-related procedures are undertaken, a subject signs and dates the informed consent form.

Interventional Clinical Trial	
A pre- or postmarket clinical investigation where the assignment of a subject to a particular medical device is decided in advance by a clinical investigation plan, or diagnostic or monitoring procedures requested in the CIP are in addition to those available as normal clinical practice and burden the subject.

Investigational Product	A preventative (vaccine), a therapeutic (drug or biologic), device, diagnostic, or palliative used as a test or comparator product in a clinical trial, including a product with a marketing authorization when used or assembled (formulated or packaged) in a way different from the authorized form, or when used for an unauthorized indication, or when used to gain further information about the authorized form.
Malfunction	Failure of an investigational medical device to perform in accordance with its intended purpose when used in accordance with the instructions for use or clinical investigation plan (CIP), or investigator's brochure (IB).
Noninterventional Study	Clinical investigation that draws inferences about the possible effect of an intervention on subjects, but the investigator has not assigned subjects into intervention groups based on a protocol and has not made any attempts to collect data on variables beyond those available throughout the course of normal clinical practice and burden to the subject.  NOTE: The term “noninterventional” is synonymous with “observational.”
Nonserious Adverse Event	Adverse event that does not meet the criteria for a serious adverse event.
Product Complaint	Any oral, electronic, or written communication that alleges deficiencies related to the identity (labeling), quality, durability, reliability, safety, effectiveness, or performance of a marketed product, including failure of the product, labeling, or packaging to meet specifications, whether or not the product is related to or caused the alleged deficiency. A complaint may allege that an adverse event or medical device malfunction has occurred.
Randomized Subject	Any subject who is assigned a randomized treatment.
Serious Adverse Device Effect (SADE)	Adverse device effect that has resulted in any of the consequences characteristic of a serious adverse event.

Serious Adverse Event (SAE)	
Adverse event that led to any of the following:
 

• Death.

• A serious deterioration in the health of the subject, users or other persons as defined by one or more of the following:

a) a life-threatening illness or injury Note: Life-threatening means that the individual was at immediate risk of death from the event as it occurred, i.e., it does not include an event which hypothetically might have caused death had it occurred in a more severe form.

b) any potentially sight-threatening event or permanent impairment to a body structure or a body function including chronic diseases.

c) inpatient hospitalization or prolonged hospitalization.

d) a medical or surgical intervention to prevent a) or b).

e) any indirect harm as a consequence of incorrect diagnostic test results when used within manufacturer's instructions for use.

• Fetal distress, fetal death, congenital abnormality or birth defect including physical or mental impairment.

 
Note: Planned hospitalization for a preexisting condition, or a procedure required by the CIP, without serious deterioration in health, is not considered a serious adverse event.
 
Refer to Section 11 for additional SAEs.

-----------------------------	--------------------------------------------------------------------------------------------------------------------------------------------------------------------------------------------------------------------------------------------------------------------------------------------------------------------------------------------------------------------------------------------------------------------------------------------------------------------------------------------------------------------------------------------------------------------------------------------------------------------------------------------------------------------------------------------------------------------------------------------------------------------------------------------------------------------------------------------------------------------------------------------------------------------------------------------------------------------------------------------------------------------------------------------------------------------------------------------------------------------------------------------------------------------------------------------------------------------------------------------------------------------------------------------------------------------------------------------------------------------------------------------------------

Serious Health Threat	
Signal from any adverse event or device deficiency that indicates an imminent risk of death or a serious deterioration in the health in subjects, users, or other persons, and that requires prompt remedial action for other subjects, users, or other persons.
 
Note: This would include events that are of significant and unexpected nature such that they become alarming as a potential serious health hazard or possibility of multiple deaths occurring at short intervals.

Significant Nonserious Adverse Event	
A significant nonserious adverse event is a symptomatic, device-related, non-sight-threatening adverse event that warrants discontinuation of any contact lens wear for greater than or equal to 2 weeks.
 
Refer to Section 11 for additional significant nonserious AEs.

Study Start	The start of the study is considered to coincide with the enrollment of the first patient.
Study Completion	The completion of the study is considered to coincide with the study-level last subject last visit or the decision to terminate the trial, whichever is later.
Unanticipated Serious Adverse Device Effect (USADE)	Serious adverse device effect which by its nature, incidence, severity, or outcome has not been identified in the risk assessment.

Use Error	
User action or lack of user action while using the medical device that leads to a different result than that intended by the manufacturer or expected by the user.
 
Note:
 

a) Use error includes the inability of the user to complete a task.

b) Use errors can result from a mismatch between the characteristics of the user, user interface, task, or use environment.

c) Users might be aware or unaware that a use error has occurred.

d) An unexpected physiological response of the patient is not by itself considered a use error.

e) A malfunction of a medical device that causes an unexpected result is not considered a use error.”

Vulnerable Subject	An individual who is unable to fully understand all aspects of the investigation that are relevant to the decision to participate, or who could be manipulated or unduly influenced as a result of a compromised position, expectation of benefits or fear of retaliatory response.

## 2 LIST OF ACRONYMS AND ABBREVIATIONS

**Table 2–1 List of Acronyms and Abbreviations Used in This Protocol**

Abbreviation	Definition
ADD	Addition
ADE	Adverse device effect
AE(s)	Adverse event(s)
ASADE	Anticipated serious adverse device effect
[REDACTED]	[REDACTED]
CFR	Code of Federal Regulations
CIs	Confidence intervals
CIP	Clinical investigation plan
CIR	Clinical investigation report
[REDACTED]	[REDACTED]
CLs	Confidence limits
cm	centimeter(s)
COL	Clinical operations lead
CRF	Case report form
CSM	Clinical study manager
D	Diopter
DEP	Data evaluability plan
ECP	Eye care professional
eCRF	Electronic case report form
EDC	Electronic data capture
EN	European Standard
FAS	Full analysis set
FDA	US Food and Drug Administration
GCP	Good Clinical Practice
HC/HI	High contrast/high illumination
HI	High
Hrs	Hours
IB	Investigator's brochure
ICF	Informed consent form
IEC	Independent ethics committee
IP	Investigational product
IRB	Institutional review board
ISO	International Organization for Standardization
LCL	Lower confidence limit
LO	Low
logMAR	Logarithm of the minimum angle of resolution
M	Meter
MED	Medium
min	minute(s)
mm	millimeter
MOP	Manual of procedures
[REDACTED]	[REDACTED]
N	Number of subjects
N/A	Not applicable

Abbreviation	Definition
NI	Noninferiority
OD	Right eye
OS	Left eye
OU	Both eyes
PI	Principal investigator
PP	Per protocol
pt	point
SADE	Serious adverse device effect
SAE	Serious adverse event
SAP	Statistical analysis plan
SD	Standard deviation
SLE	Slit lamp examination
SOP	Standard operating procedure
T30 MFfA	TOTAL30 Multifocal for Astigmatism; LID230451
UCL	Upper confidence limit
ULTRA MFfA	ULTRA Multifocal for Astigmatism
US	United States
USADE	Unanticipated serious adverse device effect
VA	Visual acuity
[REDACTED]	[REDACTED]

A horizontal bar chart with 1000 black bars. The x-axis is labeled 'Number of samples' and ranges from 0 to 1000. The y-axis is labeled 'Category' and ranges from 0 to 99. The bars are arranged in a grid, with the first 10 bars in each row. The length of each bar corresponds to the number of samples in that category. The distribution is highly skewed, with many categories having 0 or 1 sample, and a few categories having many samples. The categories are indexed from 0 to 99, and the bars are grouped by category index.

	
Safety
 

• Adverse events

• Biomicroscopy findings

• Device deficiencies

Assessment(s)	
Effectiveness
 

• HC/HI logMAR VA at distance (4 m; OD/OS/OU)                          

	
Planned number of subjects enrolled/consented: approximately 82
 
Planned number of completed subjects: 74

Sites and Locations	
Planned number of clinical sites: approximately 8
 
Planned locations (initial list of locations, which may change during start up or conduct according to study needs): US

Key inclusion criteria (See Section 8.1 for a complete list of inclusion criteria)	

• Habitual biweekly/monthly replacement soft multifocal or multifocal toric contact lens wearers aged <math>\geq</math> 40 years

• Habitual wearer in both eyes for a minimum of 5 days per week and 8 hours per day during the past 3 months

• Manifest cylinder <math>\geq</math> 0.75 D in each eye at Screening

• Willing to wear the study contact lenses for at least 8 hours per day during the treatment period and for at least 12 hours on the day before each Day 30 Follow-Up Visit

• Subject must be willing to not use readers while wearing study contact lenses for duration of the study

Key exclusion criteria (See Section 8.2 for a complete list of exclusion criteria)	

• Any use of topical ocular medications and artificial tear or rewetting drops that would require instillation during contact lens wear

• Wearing habitual contact lenses in an extended wear modality (routinely sleeping in lenses for at least 1 night per week) over the last 3 months prior to enrollment

• Monovision contact lens wearers and wearers of contact lens in one eye only

Data analysis and sample size justification	Planned Data Analysis		
	To address the primary effectiveness [REDACTED] [REDACTED] planned inferential analyses are summarized below:		
Endpoint	Comparison	Statistical Model	
Primary			
Binocular HC/HI VA at Distance	T30 MFfA vs ULTRA MFfA NI*	Mixed effects repeated measures NI margin = 0.05 (logMAR)	
[REDACTED]			

### Sample Size

Sample size calculation is based on a prior feasibility clinical study [REDACTED]

### Associated materials

- Subjects will be provided with CLEAR CARE® Cleaning & Disinfecting solution.
- Lubrication/rewetting drops will not be permitted during study lens wear. However, habitual lubrication/rewetting drop usage is allowed up to 10 minutes prior to lens insertion and any time after lens removal during the study.
- Lubrication/rewetting drops during clinic visits will only be administered per investigator discretion.
- LacriPure saline will be permitted for rinsing the lens(es) after removal and prior to insertion, if required.

**Table 3-1** Schedule of Study Procedures and Assessments

Procedure	LENS 1 (Period 1)		LENS 2 (Period 2)		Unschedule d Visit	Early Exit
	Visit 1 Screening/ Baseline/ Fit	Visit 2 Dispense Lens 1	Visit 3 Day 30 Follow-up Lens 1	Visit 4 Dispense Lens 2		
Informed consent	X					
Demographics	X					
Medical history o	X	X	X	X	X	X
Concomitant medications o	X	X	X	X	X	X
Habitual lens information (brand, power*, lens care*)	X					
■						
VA with habitual spectacles correction (OD, OS, Snellen distance)*	X				X	(X)
Keratometry (OD, OS)	X					

	LENS 1 (Period 1)		LENS 2 (Period 2)		Unschedule d Visit	Early Exit
Procedure	Visit 1 Screening/ Baseline/ Fit	Visit 2 Dispense Lens 1	Visit 3 Day 30 Follow-up Lens 1	Visit 4 Dispense Lens 2		
Autorefractometry (OD, OS, uncorrected or with study lenses)	X			X with study lenses	X with study lenses	X with study lenses
Manifest refraction	X	(X)	(X)	■	■	■
Biomicroscopy	X	X	X	X	X	X
Inclusion/exclusion criteria	X					
Randomization	X					

Procedure	LENS 1 (Period 1)		LENS 2 (Period 2)		Unschedule d Visit	Early Exit
	Visit 1 Screening/ Baseline/ Fit	Visit 2 Dispense Lens 1	Visit 3 Day 30 Follow-up Lens 1	Visit 4 Dispense Lens 2		
Visit 1 Screening/ Baseline/ Fit						
Visit 2 Dispense Lens 1						
Visit 3 Day 30 Follow-up Lens 1						
Visit 4 Dispense Lens 2						
Visit 5 Day 30 Follow-up Lens 2 / Exit						

	LENS 1 (Period 1)		LENS 2 (Period 2)		Unschedule d Visit	Early Exit
	Visit 1 Screening/ Baseline/ Fit	Visit 2 Dispense Lens 1	Visit 3 Day 30 Follow-up Lens 1	Visit 4 Dispense Lens 2	Visit 5 Day 30 Follow-up Lens 2 / Exit	
Procedure		Day 1 (Visit 2 must occur after washout with habitual spectacles, 2 to 3 days [at least 48 hours] after the end of Visit 1)	Day 1 (Visit 2 must occur after washout with habitual spectacles, 2 to 3 days [at least 48 hours] after the end of Visit 1)	(Visit 4 must occur after washout with habitual spectacles, 2 to 3 days [at least 48 hours] after the end of Visit 3)	Day 30 (-2+1 days)	Day 30 (-2+1 days)
Collect worn lenses*			X		X	(X)
Adverse events	X	X	X	X	X	X
Device deficiencies	X	X	X	X	X	X
Exit form	(X)	(X)	(X)	(X)	X	X

∞ Concomitant medications and medical history must be fully documented and collected in the subject source documents with targeted collection in the EDC.  

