### 7.2 Rationale for Study Design

This study design is justified based upon an evaluation of the results of relevant preclinical and clinical testing, as described within the IB.

The bilateral, crossover study design will ensure that the same subject is exposed to both the test and comparator lens materials during the wearing period. Therefore, [REDACTED] [REDACTED] assessments can be obtained for both lenses from the same subject.

The study will include only those subjects who are successful wearers of soft multifocal contact lenses in both eyes during the past 3 months for a minimum of 5 days per week and 8 hours per day. This will avoid confounding safety responses in non-adapted subjects. Habitual ULTRA MFfA and ULTRA for Presbyopia contact lens wearers are allowed to participate in this trial and may constitute up to approximately 50% of the total subject population. The study will exclude subjects who are monovision contact lens wearers of contact lens in one eye only.

Lubrication/rewetting drops will not be permitted during study lens wear, as this may confound the primary effectiveness and key exploratory variables. However, habitual lubrication/rewetting drop usage is allowed up to 10 minutes prior to lens insertion and any time after lens removal during the study.

Currently pregnant or lactating women and participants with any history of amblyopia, strabismus or binocular vision abnormalities will be excluded from the trial, to prevent confounding the safety/effectiveness endpoints. Subjects who become pregnant during the study will not be discontinued; however, data will be excluded from the effectiveness analyses because pregnancy can alter refraction and VA results.

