## 8.2 Exclusion Criteria

Subjects fulfilling **any** of the following criteria are not eligible for participation in this study.

1. Any anterior segment infection, inflammation, or abnormality or disease (including systemic) that contraindicates contact lens wear, as determined by the investigator.
2. Any use of systemic or ocular medications for which contact lens wear could be contraindicated, as determined by the investigator.
3. History of refractive surgery or planning to have refractive surgery during the study, or irregular cornea in either eye.
4. Ocular or intraocular surgery (excluding placement of punctal plugs) within the previous 12 months or planned during the study.

5. Biomicroscopy findings at screening that are moderate (Grade 3) or higher and/or corneal vascularization that is mild (Grade 2) or higher, and/or the presence of corneal infiltrate.
6. Current or history of pathologically dry eye in either eye that, in the opinion of the investigator, would preclude contact lens wear.
7. Current or history of herpetic keratitis in either eye.
8. Eye injury in either eye within 12 weeks immediately prior to enrollment for this trial.
9. Current or history of intolerance, hypersensitivity, or allergy to any component of the study products.
10. Currently pregnant or lactating, as stated by subject at Screening.
11. Any history of amblyopia, strabismus, or binocular vision abnormalities.
12. Any use of topical ocular medications and artificial tear or rewetting drops that would require instillation during contact lens wear.
13. The investigator, his/her staff, family members of the investigator, family members of the investigator's staff, or individuals living in the households of the aforementioned persons may not participate in the study.
14. Participation of the subject in a clinical trial within the previous 30 days or currently enrolled in any clinical trial.
15. Monovision contact lens wearers and wearers of contact lens in one eye only.
16. Wearing habitual contact lenses in an extended wear modality (routinely sleeping in lenses for at least 1 night per week) over the last 3 months prior to enrollment.

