### **10.2 Description of Study Procedures and Assessments**

Study-specific procedures and assessments described here may include standard of care; other standard of care procedures performed in the clinical management of the subject are not excluded.

Detailed descriptions of assessments and procedures are provided in the MOP. The investigator is responsible for ensuring responsibilities for all procedures and assessments are delegated to appropriately qualified site personnel.

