### **12.1 Subject Evaluability**

Final subject evaluability must be determined prior to breaking the code for masked treatment assignment and locking the database, based upon the data evaluability plan (DEP).

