### 12.2.3 Per Protocol Analysis set

The per protocol (PP) analysis set is a subset of FAS and excludes all data/subjects that have met any of the critical deviation or evaluability criteria identified in the DEP.

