# 14 ETHICS

Investigations are conducted in compliance with GCPs; international and national regulations, laws, and guidelines; EN ISO 14155; the conditions of approval imposed by reviewing IRBs/IECs or regulatory authorities; and in accordance with the ethical medical research principles outlined in the Declaration of Helsinki.

- The SOPs of the study sponsor and contract research organizations participating in the conduct of the clinical study and all other applicable regulations shall apply.
- Notifications and timelines for reporting protocol deviations should be based upon applicable ethics committee requirements.

The investigator must ensure that all personnel involved in the conduct of the study are qualified to perform their assigned responsibilities through relevant education, training, and experience. The investigator and all clinical study staff must conduct the clinical study in compliance with the protocol. The investigator is not allowed to deviate from the protocol except to protect the rights, safety, and well-being of human subjects under emergency

circumstances. Emergency deviations may proceed without prior approval of the sponsor and the IRB/IEC, but shall be documented and reported to the sponsor and the IRB/IEC as soon as possible. Deviations from this protocol, regulatory requirements, and/or GCP must be recorded and reported to the sponsor prior to database lock. If needed, corrective and preventive action should be identified, implemented, and documented within the study records. Failure to implement identified corrective and preventative actions may result in site closure by the sponsor. Use of waivers to deviate from the clinical protocol is prohibited.

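### Does the clinic-visit rule on rewetting drops open a hole in the ban on drops during study lens wear?

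*Protocol*

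**What the plan says.** Three places in the Protocol bear on this.

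- **Section 3, Associated materials.** The general rule is "Lubrication/rewetting drops will not be permitted during study lens wear". The same bullet relaxes it for the subject's own habitual drops, but only outside wear: up to 10 minutes before the lens goes in, and after it comes out. The next bullet is "Lubrication/rewetting drops during clinic visits will only be administered per investigator discretion".
- **Section 7.2, Rationale for Study Design.** The ban is repeated with its reason: "Lubrication/rewetting drops will not be permitted during study lens wear, as this may confound the primary effectiveness and key exploratory variables". The allowance before insertion and after removal is repeated too. The clinic-visit bullet is not.
- **Section 8.2, exclusion criterion 12.** Subjects are ineligible for "Any use of topical ocular medications and artificial tear or rewetting drops that would require instillation during contact lens wear".

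Section 10.2.10 schedules study-lens acuity at Visits 2, 3, 4 and 5 and at Early Exit. Procedural detail is held elsewhere: "Detailed descriptions of assessments and procedures are provided in the MOP".

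**The concern.** The ban depends on whether a lens is on the eye. The clinic bullet depends on where the subject is. These overlap, because subjects wear study lenses at the visits where acuity is measured, and the bullet does not say which rule governs the overlap. A reader could take it as an exception that lets the investigator put a drop over a worn lens shortly before the Day 30 reading. Section 7.2 says drops during wear may confound that variable.

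Record-keeping would also be at stake. If the bullet sits inside the ban, a drop given over a lens at a visit is a protocol deviation, and Section 14 requires that "Deviations from this protocol, regulatory requirements, and/or GCP must be recorded and reported to the sponsor prior to database lock". If it is an exception, the same drop complies and no deviation is logged. The per protocol set "excludes all data/subjects that have met any of the critical deviation or evaluability criteria identified in the DEP", so two sites reading the bullet differently could supply different information to the evaluability decision.

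**Working it through.** The Protocol gives no figure to reproduce here. The check is whether the statements can all hold together, and what follows if they are obeyed.

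**1. The logical form of the two rules.**

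| Rule | Source | Content |
|---|---|---|
| A | Section 3 and Section 7.2 | If a study lens is on the eye, no drop |
| B | Section 3, clinic bullet | If a drop is given at a visit, it is because the investigator decided on it |

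Rule A is a prohibition. Because of the word *only*, Rule B states a necessary condition: no drop at a visit without the investigator's decision. It does not say that this decision is sufficient, and it has no *except* or *notwithstanding*. Applied together:

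| Situation | Rule A | Rule B | Result |
|---|---|---|---|
| Lens on, away from clinic | forbids | does not apply | no drop |
| Lens on, at a visit | forbids | does not require or permit a drop over a lens | no drop |
| Lens off, at a visit | silent | needs the investigator's decision | discretionary |
| Lens off, away from clinic | silent | does not apply | habitual use, within the stated time limits |

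No row has one rule forbidding what the other demands.

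**2. Whether Rule B still has a purpose on this reading.** It does, because visits include time without lenses. Visit 1 has keratometry, manifest refraction and acuity with spectacles (Table 3-1, Section 10.2.7). Subjects arrive at Visits 2 and 4 after a spectacle washout of at least 48 hours (Section 7.1). Acuity with spectacles is repeated at exit (Section 10.2.7), and worn lenses are collected (Section 10.2.18). The preceding bullet covers the subject's own habitual drops. Rule B covers drops given in the clinic.

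**3. Whether other text favours an exception.** It does not. Section 7.2 restates the ban with its reason and mentions no clinic exception. Exclusion criterion 12 keeps out people who would need drops during wear. The exception reading would have to override, by implication, a ban stated twice.

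**4. What follows for the analysis.** If the rules are obeyed, the number of drops given over a lens before the Day 30 acuity is zero, so there is no contribution to the lens difference tested against 0.05 logMAR. For the record-keeping concern to change a result, all of these must happen:

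- an investigator gives a drop over a worn lens despite the ban;
- sites differ in how they read the bullet;
- one site logs a deviation and another does not;
- the data evaluability plan treats such a drop as critical, and does not pick it up by another route.

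None of these is shown in the Protocol. Other routes exist: medication changes are tracked throughout participation (Section 10.2.2), and use of adjunct products is reviewed (Section 10.2.19). The visible text of Section 12.4 names the full analysis set as the primary set, so the per protocol set is not the main basis for inference. The order of decisions also protects against selective handling: "Final subject evaluability must be determined prior to breaking the code for masked treatment assignment and locking the database".

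**5. Scale.** With 74 planned completers there are 74 × 2 = 148 Day 30 acuity visits (Visits 3 and 5) and 74 × 4 = 296 scheduled study-lens acuity visits (Visits 2 to 5). These count visits. They say nothing about how many would involve a drop, which may be none, so they do not measure an effect.

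**The case for a change.** The strongest opposing case is that the bullet really is silent on lens status, and no visible sentence settles it. It has no linking words in either direction. Lens wear and clinic visits overlap at exactly the visits that supply the primary endpoint. Exclusion criterion 12 is about what subjects need, not about what staff may do at a visit. Many procedural subsections refer explicitly to the manual of procedures, and this bullet does not. Section 12.5 also confines the analysis to evaluable subjects and eyes, so evaluability decisions might reach beyond the per protocol set.

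The silence stands as a fact about the wording, and the exception reading is possible. It is not an equal alternative. It needs an implied override of an express prohibition, whereas the restrictive reading needs nothing beyond the words on the page. Section 7.2 explains the design and need not repeat every operational bullet. The missing cross-reference proves little, because Section 10.2 sends procedural detail to the manual in general terms. The Section 12.5 point shows that evaluability matters. It does not show that drops are an evaluability criterion or that sites would differ.

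**Conclusion.** The concern does not hold. The clinic-visit bullet and the ban are compatible as written. The bullet narrows what may happen at visits and does not widen it, and Section 7.2 and exclusion criterion 12 agree with that. Under the plan as written, the effect on the Day 30 lens difference is zero. No effect on the per protocol set can be shown without several unsupported assumptions.

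This rests on reading *only* in its ordinary restrictive sense and on sites following the ban. The manual of procedures and the data evaluability plan are not available, and part of the Protocol is redacted. They may spell the point out further, but the conclusion does not depend on it. A clarifying clause would be harmless, but it would correct nothing that the Protocol states wrongly and would change no result. Whether drops ought to be allowed at visits is a clinical matter that is not judged here.
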